## 1.0 PROTOCOL SUMMARY AND/OR SCHEMA

Study Title	Opioid-sparing Pain Treatment In Myeloma And Lymphoma Patients Undergoing High-Dose Chemotherapy (OPTIMAL-HiChemo)
Objective	To investigate how to optimize pain management during cancer treatment by combining nonpharmacologic and pharmacologic interventions: whether using acupuncture to prevent onset of severe pain, with opioids as backup, leads to lower risk of opioid use without compromising pain management and lower symptom burden, when compared to opioids as first line treatment.
Specific Aims	1: To determine the comparative effectiveness of ACU (acupuncture and opioids, further defined below) versus OPI (opioids only) in reducing opioid use during and after HiChemo among patients who do not use opioids at baseline before HiChemo and in reducing their symptom burden during HiChemo.  2: To determine the short-term (Day 7) and long-term (Day 90) effects of ACU compared to OPI on patient-reported pain, opioid side effects (e.g. drowsiness, constipation, nausea), and quality of life among the above study population.  Exploratory: (1) Explore whether the effect of ACU treatment on Day 90 opioid use is mediated by its effect on Day 7 opioid use. (2) Explore potential heterogeneity of treatment effect (HTE) by various factors.
Study Design	A multicenter, 2-arm, parallel group, individual randomized (1:1 ratio) controlled trial comparing two pain management interventions.
Study Sites	Memorial Sloan Kettering Cancer Center, New York (MSK) Seattle Cancer Care Alliance (SCCA), Fred Hutchinson Cancer Research Center (Fred Hutch)
Interventions and Comparators	A) Acupuncture as a first-line pain preventive measure during HiChemo with opioids as back-up pain treatment (ACU), and B) opioids as first-line pain treatment (OPI). Every study patient will receive the same usual care for opioid administration, initiated and adjusted according to their pain levels as in standard of care.
Study Population	Opioid-naïve (defined as not using opioids in the week before enrollment) adult multiple myeloma, Hodgkin disease, and non-Hodgkin lymphoma patients undergoing HiChemo followed by hematopoietic stem cell transplantation (HSCT)
Total Enrollment	300
Time to Completion	36 months
Outcomes	The following will be assessed at baseline and days 7, 15, 30, and 90 after the first dose of HiChemo (Day 0):

	
Primary outcomes: opioid use, and symptom burden measured by M. D. Anderson Symptom Inventory – Bone Marrow Transplantation (MDASI-BMT).
 
Secondary outcomes: Brief Pain Inventory–Short Form, Patient-Reported Oral Mucositis Symptom Scale, Pain Medication Side Effects Questionnaire quality of life measured by Patient-Reported Outcomes Measurement Information System – 29 Items (PROMIS-29).
 
Other outcomes: opioid dose, clinical features (diagnosis and disease status), Common Terminology Criteria for Adverse Events Version 5.0 (CTC-AE v5.0), Opioid Risk Tool, Acupuncture Expectancy, use of health care resources (length of hospital stays during HSCT, transfers to the intensive care unit (ICU) while hospitalized, urgent care/emergency room visits, and readmission rates during the first 30 days post-HSCT).

Analytic Methods	All analyses will be by intent-to-treat, with patients entered into analysis as randomized, irrespective of treatment actually received. For Aim 1 opioid use, we will utilize logistic regression to model the probability of opioid use at specific time points (i.e., day 7 and 90, separately), and generalized linear mixed models to model the probability of opioid use across all time points (i.e. days 7, 15, 30, and 90), as a function of study arm (ACU vs. OPI), time, and randomization stratification variables. For Aim 1 symptom burden and Aim 2 pain, side effects and QOL , we will use linear mixed models to similarly model those continuous endpoints over time. We will also explore potential causal mechanisms by testing mediation hypotheses (e.g. test whether the effect of treatment on Day 90 opioid use is mediated through the effect of treatment on Day 7 opioid use).
Funding Source	Peer-reviewed Patient-Centered Outcomes Research Institute (PCORI) contract

## 2.0 OBJECTIVES AND SCIENTIFIC AIMS

Opioids are often used to treat acute pain during cancer treatment, yet this exposure to opioids is a risk factor for patients to become long-term opioid users. Cancer survivors have a higher risk for opioid use, with an odds ratio up to 2.55. Clinical practice guidelines all recommend a combination of pharmacologic and non-pharmacologic modalities for treatment of acute pain. But, currently there is no strong evidence guiding clinicians or patients on how best to combine the two. The proposed study in 300 patients undergoing high-dose chemotherapy (HiChemo) will generate high quality evidence to support clinicians and patients in making patient-centered decisions on the optimal management of acute pain during cancer treatment.

The overall objective is to investigate how to optimize pain management during cancer treatment by combining nonpharmacologic and pharmacologic interventions: does using acupuncture to prevent onset of severe pain, with opioids as backup, lead to lower risk of opioid use without compromising pain management and lower symptom burden, when compared to opioids as first line treatment.

Specific Aim 1: To determine the comparative effectiveness of ACU versus OPI in reducing opioid use during and after HiChemo among patients who do not use opioids at baseline before HiChemo and in reducing their symptom burden during HiChemo. Hypothesis 1 (a): ACU during HiChemo will significantly reduce the proportion of short-term opioid users (at Day 7 after HiChemo) when compared to OPI. Hypothesis 1 (b): ACU during HiChemo will significantly reduce the proportion of long-term opioid user (at Day 90 after HiChemo) when compared to OPI. Hypothesis 1 (c): ACU during HiChemo will significantly reduce the MDASI-BMT Total Symptom Severity score at Day 7 when compared to OPI.

Specific Aim 2: To determine the short-term (Day 7) and long-term (Day 90) effects of ACU compared to OPI on patient-reported pain, opioid side effects (e.g. drowsiness, constipation, nausea), and quality of life among the above study population. Hypothesis 2(a): ACU is not inferior to OPI in maintaining a low pain score at Day 7 and 90 after HiChemo. Hypothesis 2(b): ACU will reduce symptoms of drowsiness, constipation, nausea, and improve mental and physical quality of life at day 7 and 90 after HiChemo.

Exploratory Aim 1: Explore whether the effect of ACU treatment on Day 90 opioid use is mediated by its effect on Day 7 opioid use.

Exploratory Aim 2: Explore whether sex, race, ethnicity, gender, primary cancer diagnosis (MM versus HD versus NHL), Opioid Risk Tool (ORT), Acupuncture Expectancy Scale (AES) score, or concurrent use of other medications with analgesic effects influence response to interventions in this population (i.e., heterogeneity of treatment effect, HTE).

### 3.0 BACKGROUND AND RATIONALE

In 2018, an estimated 1.7 million new cases of cancer will be diagnosed in the U.S. and 0.6 million people will die from the disease. Among patients with cancer, pain is one of the most common, burdensome, and feared symptoms. A meta-analysis of 122 studies (N=4,199) showed that about 55% of patients experience pain during cancer treatment; 40% experience pain after curative treatment. Opioids are necessary and appropriate for patients with advanced cancer and intractable pain, but cancer survivors with no active cancer should not be using opioids unnecessarily. Cancer survivors have a higher risk for opioid use. A recent study using SEER and Medicare data of 46,789 older cancer survivors and 138,136 noncancer controls shows a significantly higher chronic opioid use in cancer survivors who had a higher pain burden during cancer treatment (colorectal cancer: odds ratio (OR) 1.34; 95% CI, 1.22 to 1.47; lung cancer: OR 2.55; 95% CI, 2.34 to 2.77). It takes six years for

opioid use to return to the level of controls. Other studies showed the exposure to opioids during treatment for acute pain is a strong risk factor for patients to become long-term opioid users even when the acute pain has subsided and opioids are no longer appropriate. The largest increments in probability of long-term opioid use were observed after the 5th and 31st days on short-term use. Unnecessary use of opioids presents problems beyond the medical field, such as effects on mental health, impact on family members, financial costs, opioid misuse disorder, especially in light of the current opioid crisis.

Autologous hematopoietic stem cell transplantation (auto-HSCT) is a treatment for multiple myeloma (MM), Hodgkin disease (HD), and non-Hodgkin lymphoma (NHL). Patients receive high-dose chemotherapy (HiChemo) followed by infusion of hematopoietic stem cells days later. Pain is rated one of the top five symptoms during this treatment. Oral mucositis from HiChemo is the main source of severe acute pain and the main reason patients are initiated on opioids. Between 30-43% of patients undergoing HiChemo and auto-HSCT experience severe (grade 3 or 4) mucositis which creates distress and interferes with eating and drinking. Mucositis pain follows a predictable course, usually starting shortly after HiChemo and peaking around day 7 after initiation of HiChemo. It begins to subside around days 15, and has usually resolved by Day 30. By Day 90, there should be no residual pain caused directly by HSCT. The pain can lead to periods of difficulty eating, malnutrition, dehydration, weight loss, depression, and impaired quality of life. Opioids are usually used to manage the pain. Although effective, opioids are often associated with side effects like constipation, nausea, sedation, and delirium. After mucositis has subsided, some patients may have become accustomed to opioids and use them chronically for other pain. The intensity of pain during HiChemo, the high incidence of opioid use in this population, and the predictable clinical course make HiChemo/HSCT an excellent model to study the effects of pain control interventions during cancer treatment on short- and long-term opioid use.

Pain management during cancer treatment presents patients and clinicians with a decision dilemma. The Joint Commission, American College of Physicians (ACP), National Comprehensive Cancer Network (NCCN) and American Society of Clinical Oncology (ASCO) guidelines all recommend a combination of pharmacologic (mainly opioids during HiChemo) and non-pharmacologic modalities. However there is currently no strong evidence guiding clinicians or patients on how to combine non-pharmacologic and pharmacologic interventions to manage the pain patients experience during cancer treatment. In particular, there is a lack of evidence that considers what patients perceive as important, e.g. side effects and risk of long-term opioid use.

Acupuncture is a non-pharmacologic modality that involves insertion of filiform needles into certain points on the body, followed by manual manipulation, heat, or electrical stimulation to elicit therapeutic effects. Numerous randomized controlled trials have shown its effectiveness in pain management. A systematic review of 17 trials (N= 2,027) showed that acupuncture reduced the intensity of acute and chronic low back pain more than sham acupuncture, leading ACP's clinical practice guidelines to recommend acupuncture. In a meta-analysis of 20,827 patients from 39 RCTs, the analgesic effect size of acupuncture was

0.5 SDs compared with no acupuncture control and close to 0.2 SDs compared with sham. Neuroscience research has shown that acupuncture increases production of endogenous analgesic neurotransmitters, such as endorphins and adenosine. In January 2020, Centers for Medicare & Medicaid Services (CMS) finalized a decision to cover acupuncture for Medicare patients with chronic low back pain. We conducted a pilot randomized study showing that acupuncture during HiChemo/HSCT has the potential to be an opioid-sparing non-pharmacologic therapy that significantly reduces opioid use and opioid side effects without compromising pain control. We found that patients in the sham acupuncture group had greater than five times the odds of increasing pain medications from baseline compared with those in the true acupuncture group (OR 5.31, 95% Confidence Interval (CI) 1.35 to 20.93, P=0.017). The effect was most pronounced among patients who were not taking opioids at baseline ("opioid-naïve"). In those patients, any increase in opioid use was due to the pain induced by HiChemo/HSCT, rather than from pre-existing pain. Among opioid-naïve patients, 20% (4 of 20) of those who received sham acupuncture started to use opioids during HiChemo/HSCT (Day 5), 40% around Day 30, and 25% became long-term opioid users (Day 90). In contrast, among the 15 patients who received true acupuncture, none needed to use opioids on Day 5 (p=0.119) or Day 30 (p=0.006), and only one (7%) became a long-term opioid user (Day 90, p=0.365). Acupuncture also reduces symptoms commonly associated with opioid use, such as nausea, poor appetite and drowsiness. The proposed study expands on that research and uses a patient-centered approach to address this gap in the evidence.

Patients and stakeholders took part in the formulation of the research question and the design of the study. We formed a Patient/Stakeholder Advisory Committee (PSAC) which consists of 3 patients who participated in the previous pilot study, a future HSCT patient, a patient caregiver, a representative from advocacy organization, 2 clinicians and 2 researchers. The PSAC helped with study design and development of patient-centered recruitment/retention strategies. One patient from the pilot study and one patient who is likely to receive HSCT in the near future will serve as consultants for the duration of the study.

The proposed study takes advantage of a highly efficient clinical pain model. Pain and other symptoms during HiChemo/HSCT follows a very predictable clinical course. This reduces variability and increases the statistical power of the study under a given sample size. It allows for a longitudinal evaluation of the transition from acute opioid use to chronic opioid use in each patient. The decision-making dilemma addressed by the study is commonly faced by patients and clinicians in clinical practice. The outcomes evaluated are all related to improving cancer care and patient-centered. The interventions are easy to implement. Patients, caregivers, clinicians and hospitals have a keen interest in incorporating non-drug-based pain management to reduced unnecessary opioid use. Such interest facilitates future dissemination of findings from this study. Thus, the proposed study will generate high quality evidence and potentially improve clinical practice.

[figure not shown]
## 4.0 OVERVIEW OF STUDY DESIGN/INTERVENTION

### 4.1 Design

The study is a prospective, multicenter, two-arm parallel group, individual randomized (at 1:1 ratio) controlled trial with two pain management interventions as comparators. We chose this design because it helps balance the variables between treatment arms, therefore providing stronger causal inference than an observational or non-randomized design. It also reduces bias during analysis of heterogeneity of treatment effects. The multicenter design enhances diversity of the study population and the generalizability of study results. There have been many randomized controlled trials comparing acupuncture to sham acupuncture. Its efficacy in pain control is well established. In addition, PCORI is most interested in the pragmatic aspect of clinical interventions that improve patient-centered outcomes. Thus the control group in this study is usual care, not sham acupuncture.

### 4.2 Intervention

[figure not shown]
All patients in the study will receive usual HSCT care. Patients in both the ACU group and the OPI group will receive the same usual care for opioid administration, initiated and adjusted according to their pain levels as in standard of care in the study institutions. In addition, patients in the ACU group will receive acupuncture treatment as detailed in Section 10.0. The conceptual framework is shown in the diagram in this section.

The schema of interventions and outcome assessment is as follows.

## Study Schema

## 5.0 THERAPEUTIC/DIAGNOSTIC AGENTS & NON-THERAPEUTIC ASSESSMENTS

Acupuncture is a non-pharmacologic modality that involves insertion of single-use disposable filiform needles into certain points on the body, followed by manual manipulation, heat, or electrical stimulation to elicit therapeutic effects. Acupuncture has been provided in both inpatient and outpatient settings at MSKCC for more than 15 years, as part of standard clinical services provided to MSKCC patients. Acupuncture the modality itself is not investigational. Its integration to symptom management in this clinical setting is the subject of investigation.

Seirin acupuncture needles at 30mm or 40mm and 0.16mm - 0.25 mm gauge will be used in this study. The needles are purchased and distributed from Seirin® in the United States (<http://www.seirinamerica.com>). Seirin acupuncture needles are approved by the FDA ([http://www.accessdata.fda.gov/cdrh\\_docs/pdf/K962809.pdf](http://www.accessdata.fda.gov/cdrh_docs/pdf/K962809.pdf)).

Participants in the OPI group will receive pain management with opioids administered per institutional standards.

## 6.0 CRITERIA FOR PARTICIPANT ELIGIBILITY

We will conduct the study in “opioid-naïve” multiple myeloma (MM), Hodgkin disease (HD), and non-Hodgkin lymphoma (NHL) patients who are undergoing HiChemo and autologous HSCT. In this study, “opioid-naïve” patients are defined as those who have not been taking opioids regularly in the week preceding registration to the study, not literally as those who never have taken opioids. We are targeting pain caused by chemotherapy, not severe preexisting pain caused by cancer that requires pain medication prior to HiChemo. Our preliminary data showed that those who are not taking opioids for preexisting pain before HiChemo benefitted the most from acupuncture. One-time dosing of opioids in that period for

a painful procedure (e.g. placement of a venous port) is allowed. Patients undergoing allogeneic HSCT (allo-HSCT) are not included. They tend to have more variable clinical courses and higher incidence of post-HSCT complications (infection, engraftment failure, disease relapse, or graft versus host disease).

### **6.1 Participant Inclusion Criteria**

- age 18 or older
- pathological diagnosis of MM, HD or NHL
- scheduled for high dose chemotherapy for auto-HSCT in the following month (30 days)
- not taking opioids regularly in the week prior to consent (one-time dosing of opioids for a painful procedure is allowed)

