## 13.0 CRITERIA FOR OUTCOME ASSESSMENT AND ENDPOINT EVALUABILITY

### 13.1 Criteria for Therapeutic Response/Outcome Assessment

Demographic data (age, gender, race, ethnicity, height and weight) and clinical features (cancer diagnosis, disease status, and regimen of the high-dose chemotherapy) will be collected.

Our first primary outcome is the proportion of patients who are opioid users (the number of patients using opioids at a given time divided by the total number of patients randomized to that group at Day 7 and Day 90). In this study, we define opioid user as a patient who uses any opioids during the seven days preceding the day of assessment. At baseline, patients will be asked whether they have a prescription for any opioids, any access to non-prescription opioids and whether they used any opioids in the preceding seven days. During an inpatient period, all administrations of pain medications are recorded on hospital drug administration records, which will serve as our primary data source. For outpatient, we will use pill-counting to collect this data and data on opioid dose actually consumed by the patient in the week prior to the time point (Appendix 2). Pill-counting can be done remotely with a telehealth platform.

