## **14.0 BIOSTATISTICS**

This is a multicenter, two-arm randomized controlled trial to compare the effects of two pain management strategies on opioid use, symptom burden, and other patient-reported outcomes among patients receiving high-dose chemotherapy (HiChemo) followed by HSCT. Opioid-naïve adult multiple myeloma, Hodgkin disease, and non-Hodgkin lymphoma patients undergoing HiChemo followed by HSCT will be randomized (at 1:1 ratio, see Section 7.2) to receive either acupuncture as a first-line pain preventive measure during HiChemo with opioids as back-up pain treatment (ACU), or opioids as first-line pain treatment (OPI). Study outcomes will be measured at pre-HiChemo baseline and at Days 7, 15, 30, and 90 after the first dose of HiChemo, with the Day 7 (short-term) and Day 90 (long-term) outcomes of particular interest. We expect to accrue approximately 12 patients per month, and we anticipate the study will be open to enrollment for approximately 30 months. We expect the

total study duration to be 3 years.

**14.1. Sample Size Considerations.** This study has 3 primary endpoints: opioid use at Day 7, opioid use at Day 90, and symptom burden at Day 7. The statistical plan takes that into consideration. Our overall Type I error rate for testing these 3 primary endpoints is set to alpha = 0.05. To maintain this Type I error rate, we will allocate alpha = 0.02 to each of the tests of opioid use at Day 7 and at Day 90, and we will allocate alpha = 0.01 to the test of symptom burden at Day 7.

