In our pilot study, among “opioid-naïve” patients, 25% of sham acupuncture (SA) patients and 7% of true acupuncture (TA) patients were opioid users at Day 90. For our sample size/power estimates for Aim 1, we conservatively assume that patients in the OPI arm will have similar Day 90 opioid usage (25%) as the SA patients in our prior study, and that 10% of patients in the ACU arm will be using opioids at Day 90 (slightly higher than the TA arm in our pilot study). This translates to a relative reduction of 60% fewer opioid users in the ACU arm, and an odds ratio of 0.33, which would be considered clinically meaningful. The attrition rate was only 5% in our pilot study. However, we will conservatively plan for a high 10% attrition rate by randomizing 300 patients (150 per arm) in order to obtain 270 patients (135 per arm) with evaluable Day 90 endpoints. With an initial sample size of 300 patients and a 10% attrition rate, we will have 81% statistical power to detect this Day 90 difference between the two arms (i.e. 10% vs 25%) at a significance threshold of  $p<0.02$  using logistic regression analysis and a two-sided significance test. It is possible that the OPI group will have higher opioid use than the SA patients in our pilot study, as sham acupuncture is known to have some placebo effect. We therefore expect a larger effect size than we observed in the pilot study where true acupuncture was compared to sham acupuncture. In that scenario, assuming 30% in the OPI group use opioids versus 10% in ACU group, our power will increase to 96%.

We based our sample size exclusively on having adequate power for the Day 90 comparison of opioid use. This was due to the high public health priority to find pain interventions that can reduce long-term opioid use. That said, we expect the Day 7 comparison to have similar power as the Day 90 comparison. We believe this is a conservative assumption, and that we most likely have higher power at Day 7 due to lower attrition and potentially a larger effect size at Day 7 relative to Day 90. For example, in our pilot study, 20% of sham acupuncture (SA) patients were using opioids at Day 5 (opioid usage not collected at Day 7) compared to none of the true acupuncture (TA) patients.

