**14.2.2. Specific Aim 1 Analysis Methods.** To test Aim 1 hypotheses, we will test whether ACU has fewer opioid users compared to OPI at Day 7 (Hypothesis 1a) and at Day 90 (Hypothesis 1b) using separate but similar logistic regression models. Each model will predict opioid use at the given time point as a function of treatment arm (ACU vs. OPI), controlling for the randomization stratification variables (study site and cancer diagnosis). To test whether ACU reduces symptom burden at Day 7 compared to OPI (Hypothesis 1c), we will use a LMM to model the baseline and Day 7 MDASI-BMT Total Symptom Severity scores as a function of study arm (ACU vs. OPI), time (Day 0 and Day 7), and the arm-by-time interaction (coefficient of interest), controlling for the randomization stratification variables.

**14.2.3. Specific Aim 2 Analysis Methods.** For the Aim 2 hypotheses we will first test (Hypothesis 2a) whether mean pain scores among ACU patients were non-inferior to those among OPI patients (within a non-inferiority margin of 0.34 standard deviations) at Day 7 (key Aim 2 endpoint) using a LMM containing arm, time (Days 0 and 7), and the arm-by-time interaction as predictors, controlling for the randomization stratification factors. That is, if the mean Day 7 pain score in the ACU arm is not significantly ( $p < 0.025$ ) more than 0.34 standard deviations higher than the mean OPI pain score, then we will consider ACU to be non-inferior to OPI with respect to Day 7 pain control. A similar analysis will be performed for the Day 90 pain scores. For Hypothesis 2b, we will estimate mean differences (and 95% confidence intervals) between ACU vs. OPI side effect ratings, PROMIS-29 scores, and PROMS scores using separate linear mixed models for the Day 7 and Day 90 outcomes, controlling for the randomization stratification variables and baseline score (when relevant). We will have 80% power to detect unadjusted differences between study arms on these outcomes as small as 0.34 SD (i.e., Cohen's  $d = 0.34$ ) using two-sided tests and  $p < 0.05$ . By convention, this effect size is between a small (i.e.,  $d = 0.20$ ) and moderate ( $d = 0.50$ ) effect size. We will have power to detect smaller effect sizes in the covariate-adjusted regression analyses described above, but we have insufficient preliminary data on which to base estimates of these adjusted effect sizes.

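### Eligibility admits occasional opioid users who may already meet the endpoint definition at baseline, and the collected baseline use is absent from the Day 7 and Day 90 models, which may cost power

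*Combined protocol and SAP*

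**What the plan says.** **Who is enrolled.** The Section 1.0 summary gives opioid-naïve as "defined as not using opioids in the week before enrollment". Aim 1 in Section 2.0 is to compare the arms "among patients who do not use opioids at baseline before HiChemo". Section 6.0 defines the term by absence of regular use, and Section 6.1 requires patients to be "not taking opioids regularly in the week prior to consent". Both eligibility sections allow a single dose for a painful procedure. I found no definition of regular use in the text.

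**What is counted.** Section 13.1 defines an opioid user as "a patient who uses any opioids during the seven days preceding the day of assessment". At baseline the same section has patients asked "whether they used any opioids in the preceding seven days", which is the same window and threshold as the endpoint. The data collection table in Section 11.0 marks opioid use at baseline, although the baseline list in Section 9.0 leaves it out.

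**What is modelled.** Under Section 14.2.2 the Day 7 and Day 90 logistic models contain treatment arm, "controlling for the randomization stratification variables (study site and cancer diagnosis"). Baseline opioid use is not listed. The longitudinal model of opioid use in Section 14.2.1 starts at Day 7, and baseline use is not among the effect-modifier variables in Section 14.2.5. By contrast, the symptom-burden model for Hypothesis 1c includes the baseline score, and the Hypothesis 2b models adjust for it where relevant.

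**The concern.** Eligibility turns on regular use and the endpoint turns on any use. A patient who took an opioid once or occasionally in the week before consent can be enrolled, can fall outside the population that Aim 1 names, and can satisfy the endpoint definition before the first acupuncture session.

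Two things follow. First, a Day 90 user may be a new user or someone who was already using occasionally, and no planned analysis separates the two. Hypothesis 1b is about acute treatment leading to long-term use, so the difference matters for interpretation. Second, the baseline version of a binary outcome is often prognostic for that outcome. If it is prognostic here, leaving it out of the model gives up some precision on the two opioid primary endpoints. The sample size rests on Day 90 opioid use alone, with 81% planned power, so there is little reserve.

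**Working it through.** **Inputs from the documents.** Section 14.1: "we will allocate alpha = 0.02 to each of the tests of opioid use at Day 7 and at Day 90"; Day 90 rates of 25% (OPI) and 10% (ACU); 135 evaluable patients per arm; power of 81% "using logistic regression analysis and a two-sided significance test".

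**Step 1: the plan's figure.** Use the pooled normal approximation with n = 135 and z = 2.326 (two-sided 0.02):

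power = Φ{ [|p₁ − p₂| − z√(2p̄(1 − p̄)/n)] / √([p₁(1 − p₁) + p₂(1 − p₂)]/n) }

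With p₁ = 0.25, p₂ = 0.10 and p̄ = 0.175, this is Φ{(0.150 − 2.326 × 0.0462)/0.0453} = Φ(0.94) = 82.5%. The Wald log-odds-ratio and Fisher exact versions both give 79.4%. The stated 81% is reproduced. So is the stated 96% for 30% versus 10% (pooled 96.7%, Fisher 96.0%).

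**Step 2: what the documents do not give.** They state neither the share q of patients with baseline any-use nor how strongly that use predicts Day 90 use. Both are assumptions from here on. Power with and without the covariate was obtained by simulated logistic regression (Wald test, two-sided 0.02, 135 per arm).

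**Step 3: overall rates stay at 25% versus 10%.** Gain in power from adding baseline use, in percentage points (4,000 trials per cell):

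| Baseline users q | OR = 1 | OR = 2 | OR = 4 | OR = 8 |
|---|---|---|---|---|
| 2% | −0.1 | 0.1 | 0.1 | 0.4 |
| 5% | −0.1 | 0.0 | 0.6 | 1.5 |
| 10% | 0.1 | 0.3 | 1.5 | 3.6 |
| 20% | 0.0 | 0.6 | 1.7 | 6.4 |

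OR is the odds ratio of Day 90 use for baseline users against non-users. If baseline use is not prognostic (OR = 1), adjustment neither gains nor loses anything beyond simulation error.

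**Step 4: 25% versus 10% holds only in baseline non-users.** The overall rates become (1 − q) × 0.25 + q × r₀ for OPI and (1 − q) × 0.10 + q × r₁ for ACU, where r₀ and r₁ are the Day 90 rates in baseline users. For q = 0.10 and r₀ = r₁ = 0.70 these are 0.225 + 0.07 = 29.5% and 0.09 + 0.07 = 16.0%. The Step 1 formula then gives Φ{(0.135 − 2.326 × 0.0510)/0.0504} = Φ(0.32), about 63%. Simulation (20,000 trials per scenario; 82% with no baseline users):

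| Baseline users' Day 90 rate | q | Unadjusted | Adjusted | Gain |
|---|---|---|---|---|
| 70% in both arms (no response to ACU) | 5% | 73% | 77% | 4 |
| 70% in both arms | 10% | 63% | 71% | 8 |
| 75% OPI, 50% ACU (same odds ratio as non-users) | 5% | 82% | 84% | 2 |
| 75% OPI, 50% ACU | 10% | 80% | 85% | 5 |

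Allowing a point for rounding and simulation error, the gain is roughly 2 to 9 points. Varying the common rate in non-responding baseline users from 40% to 80% (4,000 trials per cell) widens it to 1.3 to 5.1 points at q = 5% and 1.9 to 11.6 at q = 10%.

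**Step 5: how much of the loss the covariate restores.** In the non-responder rows with a 70% rate, the dilution loss is 82 − 73 = 9 points, of which 4 are recovered, and 82 − 63 = 19 points, of which 8 are recovered. So 5 of 9 and 11 of 19 points remain. With a 40% rate in baseline users most of the loss remains; with 80%, about half.

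**Step 6: validity.** With no treatment effect, an overall rate of 20% and a baseline-use odds ratio of 8, the unadjusted test rejected in 0.020 (q = 10%) and 0.018 (q = 20%) of trials, against a nominal 0.02.

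**The case against.** The planned power was computed from overall arm rates among enrolled patients, without covariates, and it reproduces. A reader might infer that 81% holds only if there are no baseline users. The documents do not support that. The assumed 25% and 10% are overall rates, and even when baseline users are added on top, unadjusted power is 80% to 82% if acupuncture works equally well in them. A reader might also infer bias. Randomisation balances baseline use in expectation, and the test keeps its size. Both parts of this objection stand.

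Neither the prevalence nor the persistence used above comes from the documents. The only irregular use the protocol names is a single dose for a procedure such as port placement, and one such dose may say little about Day 90. That stands too, and it is why the cost can be about zero. Section 6.0 does report that patients not taking opioids for pre-existing pain benefited most in the pilot, which makes a weaker effect in baseline users conceivable. That comparison does not concern one-dose users, however.

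In the least favourable scenario most of the lost power is dilution from admitting the patients, which a covariate cannot undo. This is correct and limits what the fix can promise.

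Finally, Section 6.0 gives the explicit definition and the summary may be shorthand. Even so, Aim 1 also refers to patients who do not use opioids at baseline, and no analysis targets them.

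**Conclusion.** The mismatch between eligibility, stated population and endpoint is in the text and needs no assumption. So is the absence of the collected baseline variable from the Day 7 and Day 90 logistic models, and of any analysis limited to baseline non-users.

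The effect on power is conditional. With overall rates at 25% versus 10% and 5% or fewer baseline users, omitting the covariate costs at most about 1.5 points, and nothing if baseline use is not prognostic. If 5% to 10% are baseline users with strong persistence (an assumption), adjusted power is about 2 to 9 points higher than unadjusted. Where those users do not respond to acupuncture, half or more of the dilution loss remains after adjustment, so the covariate does not bring power back to 81%.

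This is a matter of efficiency and definition. It is not an error in the sample size, a bias or a type I error problem. No Day 7 figure is given because the plan states no Day 7 rates for its power calculation. The change is worth making because the data are already collected and adjustment costs essentially no power when baseline use turns out not to matter.

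**What to change.** - **Primary models (Section 14.2.2).** Prespecify any opioid use in the seven days before the baseline assessment (yes/no) as a covariate in the Day 7 and Day 90 logistic models.
- **Sparse-cell rule.** State beforehand what happens if few patients are baseline users, for example Firth penalised logistic regression, or dropping the covariate below a set count.
- **Effect measure.** State that the adjusted odds ratio is conditional on baseline use.
- **Sensitivity analysis.** Repeat the Day 7 and Day 90 comparisons in patients with no baseline use, the population that Aim 1 names.
- **Definition.** Reconcile the meaning of opioid-naïve across Sections 1.0, 2.0, 6.0 and 6.1, and list baseline opioid use in Section 9.0 to match the Section 11.0 table.

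The cost is wording in the protocol and analysis plan; no new data are needed. The downsides are small: possible sparse cells, and a conditional rather than marginal odds ratio.
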